## Scenario summary

research topic	Application of Single-Port Robot-Assisted Breast-Conserving Surgery via Axillary Approach for Breast Cancer.
Main purpose of the study	
1. To evaluate the efficacy of single-port robots in breast cancer breast conserving surgery. Including differences in operative time and intraoperative number of lymph nodes detected.
 
2. To evaluate surgical safety: the incidence of surgical transfer and the incidence of postoperative complications.

Secondary purpose of the study	Pain and cosmetic scores of patients after breast conserving surgery under a single port robotic approach.
research design	
 Randomized controlled trial
 
 non-randomized controlled study
 
 Single-arm study
 
 Other
 
 Single-center study    multicenter study
 
Whether blind:  yes  no

subject investigated	Patients undergoing breast-conserving surgery for breast cancer.
intervention study	Single-port Robot-assisted breast-conserving surgery for breast cancer.
endpoint criteria	Success rate of breast conservation surgery under single-port robotic approach
sample capacity	Total number of cases: 100; 20 in the test group; 80 in the control group

statistical analysis	Double data entry was carried out using Excel 2010, and data analysis was performed with SPSS 25.0. The normality of continuous variables and homogeneity of variance were examined by Kolmogorov-Smirnov test and analysis of variance test respectively. For continuous variables that conformed to normal distribution and had homogeneity of variance, the independent-samples t-test was adopted. For continuous variables that did not conform to normal distribution, the Mann Whitney U test was used. For categorical variables and count data, Fisher's exact test and Pearson chi square test were employed.
Study cycle	November 2024-December 2025

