## 3. Research Design

### 3.1 Overall Study Design

-Enrollment: Subjects who meet the inclusion criteria enter the study process, including SPr-breast conserving surgery or Traditional-breast conserving surgery. The choice of the two surgical methods is based on the patients economic situation and the availability of equipment.

-Preoperative hospitalization: Collect patient disease information (including mammography, breast B ultrasound, breast enhanced MRI, etc.).

-The day of operation: Record the operation time, intraoperative bleeding volume, intraoperative complications, intraoperative adverse events, etc.

-Postoperative hospitalization: Record postoperative complications (postoperative bleeding, flap or nipple areola complex necrosis, subcutaneous emphysema, infection, capsular spasm, postoperative shoulder pain and discomfort, etc.), postoperative pain score, and postoperative pathological biopsy.

-Postoperative hospital stay: Calculated based on the number of days from surgery to discharge.

[figure not shown]
-28 days after surgery: To understand the complication rate and mortality rate within 28 days after surgery.

-90 days after surgery: To understand the complication rate and mortality rate within 90 days after surgery.

-Disease-free survival at 3 years after surgery (recurrence was defined as surgical area and distant metastasis by the time from surgery to last follow-up or date of recurrence and metastasis).

-3 year overall survival (from time from surgery to last follow-up or death).

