### 3.8 Endpoint evaluation index

To verify the safety and efficacy of the single-port robot (SPr) in breast conserving surgery, the primary endpoint of this study was the success rate of breast conserving surgery. Successful breast-conserving surgery was determined by a negative tumor margin at least 2-3mm from normal tissue, and secondary endpoints included postoperative pain score and cosmetic score.

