#### 4.4 Effectiveness analysis

The primary endpoint of this study is the success rate of breast-conserving surgery in patients with breast cancer. The success of breast-conserving surgery was determined by a negative tumor margin at least 2-3mm from normal tissue. Secondary endpoints included surgical specimen quality, functional outcome, and quality of life (postoperative pain score, postoperative cosmetic score).

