The pathology core laboratory has three professors as experts, two of the experts will independently evaluate all the pathology data of the patient, and the third expert will make the final decision in the case of inconsistent conclusions. Pathology data of all patients will be uploaded via storage media and web and evaluated by the Pathology Core Laboratory. Pathology core laboratory evaluation includes:

In addition, patient pathology interpretation before enrollment was evaluated by at least two pathologists at each subcenter, and none of the evaluators were involved in the trial execution.

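### The primary endpoint is a margin reading with a discretionary threshold, and nothing in the SAP keeps the readers unaware of which operation was done

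*SAP*

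**What the plan says.** - **Endpoint.** Section 3.8: "Successful breast-conserving surgery was determined by a negative tumor margin at least 2-3mm from normal tissue". Section 4.4 repeats that success is "determined by a negative tumor margin at least 2-3mm from normal tissue". Neither section names who makes the reading.
- **Blinding.** Under research design in the Scenario summary, the item "Whether blind" is answered no. No exception is made for outcome assessors.
- **Allocation.** Section 3.1: "The choice of the two surgical methods is based on the patients economic situation and the availability of equipment".
- **Reading procedure.** Section 7, item (11), provides three pathology experts, of whom "two of the experts will independently evaluate all the pathology data of the patient". Where those two disagree, the remaining expert adjudicates. On how the material reaches them: "Pathology data of all patients will be uploaded via storage media and web and evaluated by the Pathology Core Laboratory". The sentence that should list what the laboratory evaluates has no items after it in the text at hand.
- **Nearest safeguard.** The same item says that evaluators took no part in running the trial, but that sentence concerns pathology read before enrolment at subcentres.

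**The concern.** Surgeon and patient cannot readily be masked to robotic versus traditional surgery, so an open-label study is to be expected. A pathology reading is different, because it can be made on coded material by someone who does not know the operation.

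The SAP describes a central reading process with two readers and an adjudicator, but includes no such step. Independence between the two readers is not independence from knowledge of the treatment.

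The threshold adds to this. A margin between 2 and 3 mm meets the lower end of the stated range and fails the upper end, so the same measurement can be called success or failure. A reader who knows the operation has that discretion. The Research Background expects the single-port axillary route to do better and aims to promote its use, so an expectation exists before any data do. At stake is whether a difference in the primary endpoint, or the lack of one, could partly reflect how close margins were called.

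**Working it through.** The SAP gives no figure to reproduce here: section 4.1 states no significance level, power, success rate or margin. The check is a comparison of passages, followed by a sensitivity illustration.

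**1. Is any reader of the post-operative margin masked?**
- Scenario summary: not blind, for the study as a whole.
- Sections 3.8, 3.8.1 and 4.4: the endpoint is defined, with no assessor and no masking.
- Section 7(11): all pathology data are uploaded and read by two experts, with a third to decide. Removal of the operation, access route or surgeon is not mentioned.
- Section 7(11), last sentence: evaluators outside trial execution, but only for reading before enrolment. Being outside trial execution is also not the same as being masked.

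Result: no passage provides a masked reading of the primary endpoint.

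**2. Who reads the margin?**
The laboratory's remit over margin status follows only from the statement that its experts evaluate all the patient's pathology data. It is an inference. If the laboratory does not read the margin, the SAP names no endpoint reader at all.

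**3. Effect of one reclassified patient (1/n)**
- Robot group, n = 20 (Scenario summary and section 4.1): 1/20 = 5.0 percentage points.
- Control group, n = 60 (section 4.1): 1/60 = 1.67 points.
- Control group, n = 80 (Scenario summary): 1/80 = 1.25 points.

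The disagreement between 60 and 80 controls is a separate matter, so both are carried.

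**4. Effect on the test**
Section 4.3 plans a chi-square test, or an exact test if necessary. The values below are two-sided Fisher exact p-values. Control success rates of 80%, 90% and 95% are assumed, as is a 5% level.

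| Control successes | Robot successes | p | One more robot success | p |
|---|---|---|---|---|
| 48/60 (80%) | 19/20 | 0.167 | 20/20 | 0.031 |
| 64/80 (80%) | 19/20 | 0.182 | 20/20 | 0.037 |
| 54/60 (90%) | 13/20 | 0.015 | 14/20 | 0.064 |
| 72/80 (90%) | 14/20 | 0.032 | 15/20 | 0.129 |
| 57/60 (95%) | 15/20 | 0.021 | 16/20 | 0.062 |
| 76/80 (95%) | 16/20 | 0.049 | 17/20 | 0.141 |

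These rows were chosen because they sit at the step. Elsewhere one patient changes nothing: with 72/80 controls, 17/20 gives p = 0.689 and 18/20 gives p = 1.0. So one margin call can change the conclusion, but need not.

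**The case against.** The case against has several parts.

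- **Unmasked reading is inferred.** No sentence says that readers are told the operation. A study-level no under blinding correctly describes an open-label study, and reader masking may be set out in a protocol or laboratory manual not at hand. It is true that this is an inference. But the SAP itself addresses blinding and sets out the reading procedure, and it leaves the step out of both. Amending the summary would be a clarification and not the correction of a false statement.
- **The laboratory may not read margins, or may not exist.** A reader might infer from 7(11) that a working laboratory already reads this endpoint, so that masking would cost nothing. The document does not support that. The list of evaluations is empty in the text at hand. Section 7 also speaks of subcentres, a multi-centre committee and gastrointestinal surgeons, although the Scenario summary and section 4.2 describe a single-centre breast study. The text may have been carried over from another study. This part stands, and it makes the fix conditional.
- **Two readers and an adjudicator already limit bias.** They limit random error and the influence of any one reader. They do not remove a leaning that all three share.
- **Masking is not the only remedy.** A reader might infer that it is the single place where bias on this endpoint can be reduced. It is not. Fixing one threshold reduces discretion directly. Exclusion criterion 4 (margin still not assured negative after re-resection) and exit criterion 1 (conversion from robotic surgery) can remove unfavourable cases whatever the readers know. This part stands.
- **The 5-point figure is not a bias estimate.** Correct: it is group-size arithmetic and applies to a reclassification for any reason.

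**Conclusion.** The point holds in a limited form. The primary endpoint is a margin judgement with room for discretion, in a non-randomised study declared not blind, and the described reading process has no step that withholds the operation. An avoidable source of assessor bias is left open.

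One robot patient read differently moves that group's rate by 5 points, against 1.67 or 1.25 points for a control, and in some assumed scenarios this carries the test across 5%. A reader might go further and infer that the robot group's rate will be inflated by some number of points. The document does not support this: it gives no frequency of close margins or of reader disagreement, so neither the size nor the direction of any bias can be estimated.

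The conclusion rests on two assumptions: that the core laboratory, or some other pathologist, makes the reading that decides the endpoint, and that no document outside the SAP already masks that reader. Masking would remove one possible bias. Confounding from a choice of operation driven by economic situation and equipment availability would remain.

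**What to change.** 1. In section 7(11), complete the list of core-laboratory evaluations and include margin status and distance for the primary endpoint.
2. In 7(11) and 3.8, state that the two readers and the adjudicator determine this endpoint on slides and measurements identified by a study number only, with operation, access route and surgeon removed, and that this reading is the one analysed.
3. In 3.8 and 4.4, replace the range by one pre-specified reading of the threshold, applied to both groups. Which value to use is for the investigators to decide.
4. In the Scenario summary, describe the study as open-label with masked assessment of the primary endpoint.
5. Confirm that the laboratory described in section 7 exists for this single-centre study. If it does not, name the pathologists who will make the masked reading.

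The cost is a small relabelling effort for slides and request forms, with no added patient or procedure. If the laboratory does not exist, readers would have to be found, and the cost would be higher.

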## VIII. Risk / benefit assessment

### 8.1 Benefits (personal and social benefits)

As a new surgical method, single-port robot breast-conserving surgery is still in

continuous exploration. Surgery-related risks and complications such as intraoperative and postoperative hemorrhage, flap or nipple areola complex necrosis, subcutaneous emphysema, infection, capsule and capsular spasm, and postoperative shoulder pain and discomfort may occur during the surgical procedure and perioperative period. The difference between SPr-breast conserving surgery and open breast conserving surgery is that the surgical approach is different and the surgical procedure and principles are basically the same. In the early stage, our department has carried out more than 200 cases of Da Vinci multi-arm robotic (Xi or Si surgical system) surgery, accumulated the experience of robotic surgery, and verified the feasibility and safety, and laid a solid foundation for the smooth development of this study.

This study aims to evaluate the safety and feasibility of a single-port robot-assisted transaxillary breast-conserving procedure and to evaluate the clinical efficacy of this procedure. Comparanalysis of the intraoperative complications, postoperative complications, perioperative recovery effect and safety of breast cancer with single hole robot and open surgery, so as to choose a more effective and safe surgical method.

## **8.2 Risks (indicating the possible risk probability, measures to minimize the possible range)**

Surgery is invasive, so the risk exists in the postoperative complications of surgical procedures under equivalent conditions. Therefore, patients are tested for complications and treated for complications in time.

## **9. Ethics Principles and requirements for clinical research**

This study will be performed strictly in accordance with clinical trial specifications, GCP principles and the Declaration of Helsinki. The informed consent will be signed by the attending physician or a qualified, strictly trained and authorized clinical staff. The trial procedure should be explained to the subject and / or authorized person and give the subject and / or authorized person sufficient time (at least 72 hours) to consider participation.

### **(1) Information provided to the patient or agent includes:**

-Statement that the trial involves the study

- To fully and impartially explain the procedures to be followed
- Full description of the nature, expected duration, and purpose of the study
- Describe any foreseeable risks or discomfort caused to the patient
- Description of any benefits that can be reasonably expected
- Patient data will be declared as carefully handled and confidential, and the duration of data storage (15 years).
- Note that participation is voluntary, refusal to participate will not result in punishment or loss of the benefits and rights of the patient, and that the patient may stop participation at any time without punishment or loss of relevant rights, in which case the patient will receive standard treatment and an equivalent degree of care.

### **(2) Statement of conflict of interest**

There is no personal or non-financial interest between the investigator and the subject.

## 10. Research progress

November 2024- -June 2025: screen the enrolled patients and complete the preliminary preparation of the project

July 2025-October 2025: Patient data are collected and processed

November 2025- -December 2025: Write the result report

